5.2. Primary and Final Analyses

The primary analysis of this study will be performed when the last participant in the study has reached study visit Week 48 or has discontinued earlier.

The final analysis will be performed when all participants in the study (both parts if Part 2 of the study has started) have reached the final study visit FU Week 48 or have discontinued earlier.

5.3. Primary Efficacy Endpoint

5.3.1. Definition

The primary efficacy endpoint is defined as the proportion of participants with normal ALT (defined as ALT < ULN with ULN = 34 U/L for female and 43 U/L for male) in combination with HDV RNA $\geq 2 \log_{10}$ IU/mL decline from baseline and/or HDV RNA TND at Week 48.

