5.4.2.1. Definition

The second key secondary efficacy endpoint is defined as the proportion of participants with normal ALT at Week 48.

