5.4.2.2.1. Main Estimator of the Main Estimand for the KSE2

5.4.2.2.1.1. Analysis Methods

Statistical Model

The same stratum-adjusted MH test on the difference of proportions as described for the main estimator of the main estimand for the primary endpoint will be used (see Section 5.3.2.1).

5.4.2.2.1.2. Data Included

All available data from ITT analysis set in Part 2, after taking into account all the ICEs and applying the ICE strategies specified in the previous Section 5.4.2.2, will be included.

5.4.2.2.1.3. Assumptions

- Missing Data for ALT are Missing At Random (MAR)
- The treatment effect is homogeneous across strata

5.4.2.2.1.4. Missing Data Handling Rule

- Participants who withdraw from the study prior to Week 48 will be considered as non-responders.
- For participants who remain in the study at Week 48 after experiencing a major protocol deviation defined for the purpose of efficacy analyses, which is an ICE, and have missing ALT at Week 48, then the imputation to non-response will be applied. If the ALT value for the KSE2 at Week 48 is available, then such data will be used to determine their response status.

- For participants who remain the study at Week 48, have had no major protocol deviations defined as ICE and have the values of ALT available, such data will be used to determine their response status.
- For the participants who remain in the study at Week 48 and who have not experienced any major protocol deviations defined for the purpose of efficacy analyses as ICE, and has missing ALT values missing at Week 48, then missing data will be imputed by the values obtained from the MI model performed for the main estimator of the primary efficacy endpoint to leverage the correlations between HDV RNA and ALT values (see Section 5.3.2.1.4). Once the ALT values at Week 48 are obtained, the binary key secondary endpoint will be derived and analyzed as described in Section 5.3.2.1.

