5.4.2.2.4. Main Estimator of the Supplementary Estimand for the KSE2

5.4.2.2.4.1. Analysis Methods

Statistical Model

Similar stratum-adjusted MH test on the difference of proportions as described for the main estimator of the main estimand will be used (see section 5.4.1.2.1).

5.4.2.2.4.2. Data Included

All available data from randomized participants in Part 2 that are included in the mITT analysis set will be used, after taking into account the ICEs and applying the ICE strategies specified in Section 5.4.2.2.

5.4.2.2.4.3. Assumptions

- The treatment effect is homogeneous across strata

5.4.2.2.4.4. Missing Data Handling Rule

Participants who withdraw from the study prior to Week 48 will be considered non-responders. For the participants who remain in the study at Week 48 and who have not experienced an ICE as listed in 0, but with ALT values missing at Week 48, then the method to handle missing data will be the imputation to non-responder.

5.4.3. KSE3: HBsAg Seroclearance at Week 48

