5.5.1.3. Time to Event Endpoints

5.5.1.3.1. Time to Event Endpoints Based on Parameters Used in Key Secondary Endpoints

All time to event endpoints will analyzed throughout the entire study (and not by study phase) using DB day 1 as reference timepoint by study part.

5.5.1.3.1.1. Time to HDV RNA $\geq 2 \log_{10}$ IU/mL Decline or HDV RNA TND or <LLOQ

Time to reach HDV RNA $\geq 2 \log_{10}$ IU/mL decline or HDV RNA TND is defined as the number of days between the date of first study intervention intake and the date of the first occurrence of HDV RNA $\geq 2 \log_{10}$ IU/mL decline or HDV RNA TND, whichever event is first (i.e. \min [the date of the first HDV RNA $\geq 2 \log_{10}$ IU/mL decline, date of the first time HDV RNA is TND] – the date of first study intervention intake + 1). The participants who withdrew early from the study before achieving such event, or who did not achieve it at the time of the cut-off date for the analysis will

be censored at the last available HDV RNA assessment during the study or the cut-off date, whichever comes first.

5.5.1.3.1.2. Time to HDV RNA $\geq 2 \log_{10}$ IU/mL Decline

The same derivation and censoring rules as in Section 5.5.1.3.1.1 apply for the time to reach HDV RNA decline $\geq 2 \log_{10}$ IU/mL, which will be calculated using the date of first HDV RNA decline $\geq 2 \log_{10}$ IU/mL.

5.5.1.3.1.3. Time to HDV RNA TND or <LLOQ

The same derivation and censoring rules as in Section 5.5.1.3.1.1 apply for the time to reach HDV RNA TND and time to reach HDV RNA < LLOQ, which will be calculated using the date of first HDV RNA TND and date of first HDV RNA < LLOQ respectively.

5.5.1.3.1.4. Time to Normal ALT Levels

The same derivation and censoring rules as in Section 5.5.1.3.1.1 apply for the time to reach normal ALT (i.e. ALT value \leq ULN), which will be calculated using the first date of normal ALT value.

5.5.1.3.1.5. Time to HBsAg Thresholds

The following thresholds will be evaluated:

- HBsAg < LLOQ (i.e seroclearance)
- HBsAg < 1 IU/mL
- HBsAg < 10 IU/mL
- HBsAg < 100 IU/mL
- HBsAg decline $\geq 2 \log_{10}$ IU/mL

The same derivation and censoring rules as in Section 5.5.1.3.1.1 apply for the time to reach HBsAg thresholds, which will be calculated using the date of first occurrence of the given HBsAg threshold.

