5.6.1.3.1. Time to Undetectability of HBcrAg

The same derivation and censoring rules as in Section 5.5.1.3.1.1 apply for the time to undetectability of HBcrAg, which will be calculated using the date of first HBcrAg TND.

Only the participants with HBcrAg values \geq LLOQ+ 0.5 \log_{10} U/mL (i.e. $\geq 3.5 \log_{10}$ U/mL) at baseline will be included in this analysis.

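### Normal ALT is below the ULN in the primary endpoint but at or below it in time to normal ALT, which also admits participants already normal at baseline

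*SAP*

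**What the plan says.** Section 5.3.1 builds the primary endpoint on "normal ALT (defined as ALT < ULN with ULN = 34 U/L for female and 43 U/L for male", a strict inequality. Section 5.5.1.3.1.4, under the other secondary time-to-event endpoints, describes the time to "reach normal ALT (i.e. ALT value \leq ULN", a non-strict one. The date rule there is "which will be calculated using the first date of normal ALT value", with the derivation and censoring of Section 5.5.1.3.1.1, so time runs from first study intervention intake. No condition on baseline ALT is attached.

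KSE2 restates no cut-off: "The second key secondary efficacy endpoint is defined as the proportion of participants with normal ALT at Week 48" (Section 5.4.2.1). Its main estimator uses "All available data from ITT analysis set in Part 2" (Section 5.4.2.2.1.2). The combined endpoints over time (5.5.1.1.1), sustained HDV response (5.5.1.1.6), the matched-exposure endpoints (5.5.1.4) and the exploratory repeats (5.6.1.1.1) also refer to normal ALT without a cut-off.

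The ALT categories in Sections 2.4.1, 4.2.1 and 5.5.1.1.1 have ≤1.0xULN as their lowest class.

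Other time-to-event endpoints do condition on baseline. For HBcrAg undetectability, Section 5.6.1.3.1 begins "Only the participants with HBcrAg values" and sets a floor of 3.5 log10 U/mL at baseline. Appearance of anti-HBs and of anti-HBe (5.6.1.3.2 and 5.6.1.3.3) requires a baseline value below LLOQ or a negative baseline result.

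**The concern.** There are two separate faults.

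First, one term has two operators. A value exactly at the ULN is not normal for the primary endpoint, is normal for time to normal ALT, and is unspecified for KSE2 and the remaining normal-ALT endpoints. Tables in the same report could then disagree about the same participant, and the choice for KSE2 would fall to the programmer. With about six controls in Part 2, one participant is visible in the result.

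Second, time to normal ALT is meant to describe how quickly ALT becomes normal. A participant who is normal at baseline has nothing to normalise, yet contributes an early event to the Kaplan-Meier curve, the median and the log-rank test planned in Section 5.5.2.3. To that extent the curve reflects the baseline ALT mix of the arms and not the regimen.

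**Working it through.** The SAP gives no figure of its own on this point, so the check sets the passages side by side and adds simple arithmetic.

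**Classification of a value exactly at the ULN (34 U/L female, 43 U/L male)**

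| Use | Section | Rule | Result at the ULN |
|---|---|---|---|
| Primary endpoint | 5.3.1 | < ULN | not normal |
| Time to normal ALT | 5.5.1.3.1.4 | ≤ ULN | normal |
| ALT categories | 2.4.1, 4.2.1, 5.5.1.1.1 | ≤1.0xULN | lowest class |
| KSE2 | 5.4.2.1 | none restated | undetermined |
| Other normal-ALT endpoints | 5.5.1.1.1, 5.5.1.1.6, 5.5.1.4, 5.6.1.1.1 | none restated | undetermined |

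**Weight of one boundary participant in KSE2**

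- Inputs: 30 participants in Part 2 and 4:1 allocation (Section 1.2). The split by arm is not stated; 4:1 implies 30 × 4/5 = 24 and 30 × 1/5 = 6.
- Arm 1: 100/24 = 4.2 percentage points.
- Arm 2: 100/6 = 16.7 percentage points.

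**Effect of participants normal at baseline on time to normal ALT**

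- Event time = date of first normal ALT − date of first intake + 1 (5.5.1.3.1.1, applied through 5.5.1.3.1.4).
- For a participant normal at baseline, the event falls at the first normal visit. The first post-baseline time point in Table 2 is Week 2, target Day 15.
- Section 5.1 reports the 25th percentile, median and 75th percentile. If such participants are still normal at the first visit, 2 of 6 in Arm 2 (33%) are enough to put that arm's 25th percentile there. In Arm 1, 7 of 24 (29%) would do the same. No response to treatment is needed in either case.
- How many participants this concerns is unknown. The SAP lists ≤1.0xULN as a baseline category. The only ALT entry limit it shows is the upper one: in Attachment 1, a screening ALT of at least 10xULN is a deviation. Any lower limit would be in the protocol.

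**Comparison within the plan**

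HBcrAg undetectability, anti-HBs appearance and anti-HBe appearance each carry a baseline condition. Time to normal ALT is a time-to-first-occurrence endpoint of the same kind and carries none.

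**The case against.** The strongest reply is that little depends on this. Section 5.3.1 fixes both the operator and the numeric limits for the primary endpoint. The ≤ wording defines normal ALT in only one other secondary endpoint, and the categories are class boundaries. Only values exactly at the limit are affected, and Section 1.3 makes the analyses descriptive. KSE2 is defined as normal ALT at Week 48, not as normalisation. Staying normal is informative in a trial where the rationale for SAP Amendment 3 reports on-treatment ALT elevations in about half of Part 1. KSE2 by baseline ALT class is already planned (2.4.1 and 5.4.5), subject to the subgroup size rules.

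Most of this stands, and it rules out several stronger readings:

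- A reader might infer that the primary responder count is ambiguous. It is not, because Section 5.3.1 says what to program.
- A reader might attach a probability that a boundary value changes a primary response. That needs an ALT distribution the SAP does not give. It would also have to allow for the HDV RNA component and for discontinuation counting as non-response (5.3.2).
- A reader might infer that 20% normal at baseline makes 20% of the time-to-normal events spurious. That does not follow. If 40% of the others normalise (assumed), the share is 0.20/(0.20 + 0.80 × 0.40) = 0.20/0.52 = 38%. The true share depends on two unknowns.
- A reader might infer that KSE2 wrongly includes participants normal at baseline, or that the heading "Main Estimator of the Supplementary Estimand for the KSE2" implies a missing normalisation estimand. The first is a choice of endpoint. The text under that heading gives a model, the mITT set and a missing-data rule, and largely repeats Section 5.4.2.2.3.

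The point about class boundaries stands only in part. Section 1.1 lists the proportion with normal ALT as an other secondary endpoint, and the only stand-alone ALT entry in Section 5.5.1.1.1 is the categorisation. For that endpoint the ≤1.0xULN class may well serve as the definition of normal.

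**Conclusion.** Both faults hold on the text. The operator mismatch is narrow: it affects only values exactly at the ULN. It leaves the primary endpoint unaffected if Section 5.3.1 is followed, and it leaves KSE2 undetermined at the boundary. There, one participant is worth about 4.2 points in Arm 1 or 16.7 points in Arm 2, assuming a 24:6 split.

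The missing at-risk restriction matters more, because following Section 5.5.1.3.1.4 as written gives a distorted time-to-normalisation result whenever anyone is normal at baseline. The SAP provides for such participants without showing how many there are, so the size of the distortion cannot be stated. No formal conclusion depends on either fault, since the analyses are descriptive, but the estimates, confidence intervals and log-rank results would still be reported.

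**What to change.** 1. State one definition of normal ALT, with its operator and sex-specific limits, and cross-reference it in Sections 5.3.1, 5.4.2, 5.5 and 5.6. Keeping the strict rule of Section 5.3.1 leaves the primary endpoint untouched; the ALT categories then need either a matching boundary or a footnote. Adopting ≤ ULN matches the categories but alters the primary definition. Because Part 2 participants are unblinded individually after Week 48 (Section 1.5), that change would need a dated justification.
2. In Section 5.5.1.3.1.4, restrict the analysis to participants with abnormal ALT at baseline under the chosen definition, and report how many are excluded in each arm.
3. Leave KSE2 on the whole Part 2 ITT set. A descriptive summary in the subset with abnormal baseline ALT may be added but is not required.

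The cost is a short SAP text change and a smaller denominator for time to normal ALT, which could leave very few controls in Part 2. No new data are needed.

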5.3.2. Main Estimand for the Primary Endpoint

Primary Study Objective: To evaluate the efficacy of JNJ-3989 + NA regimen versus Placebo + NA in reducing HDV replication and associated liver inflammation.

Scientific question: in the adult non-cirrhotic population co-infected with HBV and HDV, what is the benefit of JNJ-3989 (100mg Q4W) in combination with NA compared with Placebo + NA for 48 weeks in reducing HDV replication measured by HDV RNA and liver inflammation measured by ALT?

The main estimand for the primary endpoint is characterized by the following attributes:

A) Study Intervention:

- Arm 1: JNJ-3989 + NA
- Arm 2: Placebo + NA

B) Study population: Non-cirrhotic patients 18 to 65 years of age, inclusive, with HBV/HDV co-infection

C) Variable: Response status defined as having HDV RNA decline $\geq 2 \log_{10}$ IU/mL from baseline or HDV RNA TND in combination with normal ALT at Week 48

D) Intercurrent events (ICEs):

- Treatment discontinuation prior to Week 48: if the participant discontinued treatment prior to Week 48 then the participant will be considered as non-responder (composite strategy).
- Selected major protocol deviations affecting efficacy: 0 identifies deviations considered ICE. Participants with such deviations and who have missing ALT and/or HDV RNA data for the primary endpoint at Week 48 will be considered as non-responders (composite strategy).
- Deaths prior to Week 48 are handled in a composite strategy as participants who die prior to Week 48 will be considered as non-responders.

E) Population level summary: Difference in proportion of responders defined by the primary endpoint between the two intervention arms (Arm 1 – Arm 2).

5.3.2.1. Main Estimator of the Main Estimand for the Primary Endpoint

5.3.2.1.1. Analysis Methods

Statistical Model

The proportion of responders will be compared between the 2 arms using the stratum-adjusted Mantel-Haenszel (MH) test on the difference of proportions, with the following stratification factors: HDV RNA testing laboratory location (China versus outside China) and HBeAg status at screening (positive vs negative).

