1.3. Statistical Hypotheses for Trial Objectives

The original protocol had as primary hypothesis of this study that the combination regimen of JNJ-3989 + NA has superior efficacy compared to NA treatment alone in reducing HDV replication and improving the associated liver inflammation, as measured by the primary efficacy endpoint at Week 48 (the proportion of participants with HDV RNA decline ≥ 2 log₁₀ IU/mL from baseline or HDV RNA TND in combination with normal ALT at Week 48). Due to the decision to stop enrollment at 30 participants in Part 2 of the study (see Section 1.2), the primary study hypothesis can no longer be tested with sufficient power, and hence the statistical analyses will be descriptive.

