1.4. Sample Size Justification

A total sample size of 130 participants for Part 2 in the original protocol would have yielded a statistical power >90% to detect a between-arm difference of $\geq 26\%$ in the primary efficacy endpoint at Week 48, at a 1-sided Type 1 error rate of 0.025, based on the test for the between-arm difference in proportions with the normal approximation. Per Protocol Amendment 4, the sample size in Part 2 was reduced to 30 participants. In the original protocol, sample size re-estimation was planned at the single IA during Part 2 to allow for an increase to a maximum of 170 participants in Part 2 for the conditional power at the end of the study to be at least 80% in case the assumed 0.04 response rate for placebo was too conservative. Due to reduction in sample size per Protocol Amendment 4, the single IA with sample size re-estimation was removed. In the original protocol, the number of participants included in this study was planned to be a minimum of approximately N=20 (if Part 2 is not initiated) or between a minimum of N=165 and a maximum of N=190 if Part 2 is initiated. Per Protocol Amendment 4, the planned number of participants included in the study will be N=20 in Part 1 and N=30 in Part 2.

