The potential association between the primary efficacy endpoint and the selected demographic and baseline characteristics (in Section 2.4.1) will be explored using a logistic regression model which will be estimated for each subgroup variable, one at a time. The factors in each model will be treatment arm, the randomization stratification factors, the subgroup variable, and the treatment-by-stage and treatment-by-subgroup variable as the interaction-terms. The Firth's penalized likelihood method^{9,10} (as implemented in SAS PROC LOGISTIC) will be used in the logistic regression to reduce possible bias which could arise in the presence of a zero-response rate in one or more subgroup levels and/or intervention arms.

Corresponding 95% CIs will be also calculated. A forest plot will present graphically the endpoint estimates resulting from the models described above, by treatment arm and the prespecified subgroup levels, with the corresponding 95% CIs.

5.4. **Key Secondary Endpoints (KSE)**

All key secondary endpoints will be summarized individually by intervention arm, stage and study parts (Parts 1 and 2, as well as for the whole study data overall). The statistical analysis will follow the estimand and estimators framework as described in the following sections. Testing will be performed by providing adjusted p-values as per Section **Error! Reference source not found.**

5.4.1. KSE1: HDV RNA Decline from Baseline $\geq 2 \log_{10}$ IU/mL or HDV RNA TND at Week 48

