5.5.2.1. Binary Endpoints

The binary endpoints will be analyzed using the stratum-adjusted MH test similar to the primary efficacy endpoint with corresponding 95% CIs on the difference of proportions.

The number and proportion of participants achieving the endpoints defined in Section 5.5.1.1 will be summarized over time with associated 95% CI. Between-arm difference in proportions with 95% CI will also be provided for all timepoints.

Bar charts will be provided for proportions in each intervention arm.

Cumulative percentage of participants achieving any given decrease from baseline at Week 48 in selected virology markers (e.g. HBsAg, HBV DNA etc.) will be presented graphically.

Subsections below describe the additional analyses planned for only those specific other secondary binary endpoints that require further evaluations.

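### With about six controls in Part 2, the stratified Mantel-Haenszel difference needs a named small-sample confidence interval; the usual large-sample ones give a zero-responder placebo arm no uncertainty

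*SAP*

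**What the plan says.** SAP Section 5.3.2.1.1 states for the primary endpoint: "The proportion of responders will be compared between the 2 arms using the stratum-adjusted Mantel-Haenszel (MH) test on the difference of proportions". The strata are HDV RNA laboratory location (China or elsewhere) and HBeAg status at screening, so there are up to four. Section 5.3.2.1.2 restricts the analysis to the Part 2 ITT set. The main estimators of KSE1 to KSE4 (Sections 5.4.1.2.1.1, 5.4.2.2.1.1, 5.4.3.2.1.1 and 5.4.4.2.1.1) refer back to this method. Section 5.5.2.1 says the other binary endpoints are "analyzed using the stratum-adjusted MH test similar to the primary efficacy endpoint with corresponding 95% CIs on the difference of proportions". Those endpoints include the primary composite followed over time (Section 5.5.1.1.1).

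No section names a variance estimator or interval method for the difference, or a rule for zero cells or for strata with only one arm. Firth's penalty for zero-response arms appears only in the subgroup logistic models (Section 5.3.3).

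On the status of inference, Section 1.3 says that "the primary study hypothesis can no longer be tested with sufficient power, and hence the statistical analyses will be descriptive". Section 5.4 nevertheless says "Testing will be performed by providing adjusted p-values as per Section", followed by a broken cross-reference.

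**The concern.** The original justification in Section 1.4 was large-sample: the power was "based on the test for the between-arm difference in proportions with the normal approximation", for 130 participants. At 30 participants the control arm has about six people spread over up to four strata, and the expected number of placebo responders at 4% is 6 x 0.04 = 0.24. A large-sample variance for the difference estimates the placebo contribution from the observed placebo proportion. When that proportion is zero, so is the contribution, although six participants say little about the true rate.

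In a descriptive study the reader relies on the estimate and its interval. An interval that is too narrow in the most likely outcome can look like clear superiority. A second effect is that a stratum with participants from only one arm gets no Mantel-Haenszel weight, so those participants leave the estimate although they belong to the ITT set.

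**Working it through.** **Inputs.** Part 2 N = 30 and placebo rate 0.04 (Section 1.4). Allocation 4:1 (Section 1.2), hence 24 vs 6; this split is derived, as the SAP does not state the arm sizes. Target active rate 0.30 (Attachment 3), so the difference is 0.30 - 0.04 = 0.26, as in Section 1.4.

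**Reproducing the plan's figure.** Section 1.4 claims power above 90% with 130 participants for a true difference of 26 percentage points or more, "at a 1-sided Type 1 error rate of 0.025". With 104 vs 26:
- Pooled rate = (104 x 0.30 + 26 x 0.04)/130 = 0.248.
- Null SE = sqrt(0.248 x 0.752 x (1/104 + 1/26)) = 0.0947.
- Alternative SE = sqrt(0.30 x 0.70/104 + 0.04 x 0.96/26) = 0.0591.
- Power with pooled variance = Phi((0.26 - 1.96 x 0.0947)/0.0591) = 89.6%. With unpooled variance it is 99.3%.

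The stated power above 90% is therefore reproduced to within rounding, and the inputs are read correctly.

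**Probability of no placebo responders.** 0.96^6 = 0.783. The exact 95% upper limit for 0/6 is 1 - 0.025^(1/6) = 45.9%.

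**Interval when placebo is 0/6.** In a single stratum, Greenland-Robins and Sato both reduce to sqrt(p1(1 - p1)/24) when p0 = 0. For 7/24, p1 = 0.292 and SE = sqrt(0.292 x 0.708/24) = 0.0928, so the interval is 0.292 ± 1.96 x 0.0928 = 0.110 to 0.474. Newcombe uses the Wilson limits 0.149 to 0.492 for 7/24 and 0 to 0.390 for 0/6. Its lower limit is 0.292 - sqrt((0.292 - 0.149)^2 + 0.390^2) = -0.124.

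| Arm 1 vs 0/6 | MH, large-sample variance | Newcombe | Miettinen-Nurminen | Fisher p (two-sided) |
|---|---|---|---|---|
| 0/24 | 0 to 0 | -0.390 to 0.138 | -0.398 to 0.142 | 1.00 |
| 3/24 | -0.007 to 0.257 | -0.274 to 0.310 | -0.287 to 0.314 | 1.00 |
| 4/24 | 0.018 to 0.316 | -0.236 to 0.359 | -0.249 to 0.362 | 0.56 |
| 7/24 | 0.110 to 0.474 | -0.124 to 0.492 | -0.134 to 0.495 | 0.29 |
| 10/24 | 0.219 to 0.614 | -0.010 to 0.612 | -0.016 to 0.615 | 0.07 |
| 11/24 | 0.259 to 0.658 | 0.029 to 0.649 | 0.024 to 0.652 | 0.06 |

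The Mantel-Haenszel chi-square, which uses a null variance, has p = 0.29 at 4/24, 0.057 at 10/24 and 0.041 at 11/24. From 4 to 10 responders the test and a large-sample interval would therefore disagree.

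Stratifying hardly changes this. For (1/4 vs 0/1) plus (6/20 vs 0/5), the interval is 0.110 to 0.473 (Greenland-Robins) or 0.110 to 0.474 (Sato).

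**Operating characteristics.** Full enumeration of Binomial(24) x Binomial(6), one stratum, no missing data. The table gives the chance that the lower limit exceeds zero when both arms share the same true rate (nominal 2.5%):

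| Common rate | MH, large-sample variance | Newcombe |
|---|---|---|
| 0.04 | 1.1% | 0.0% |
| 0.10 | 11.4% | 0.0% |
| 0.15 | 18.7% | 0.01% |
| 0.20 | 19.3% | 0.1% |
| 0.30 | 11.6% | 0.9% |

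Up to a rate of 0.20, practically all of the Mantel-Haenszel error comes from 0/6 outcomes. Two-sided coverage at 0.30 vs 0.04 is 93.7% (Newcombe 96.0%). At 0.30 vs 0.10 it is 90.1% (Newcombe 95.3%).

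**Pooled Parts 1 and 2.** 52 participants (Section 1.2) at 4:1 are about 42 vs 10. Then 0.96^10 = 0.66, and the same enumeration gives false exclusion of 5.7% at a common rate of 0.04 and 21% at 0.10. Pooling does not cure the problem.

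**One-arm strata.** The Mantel-Haenszel weight is n1 x n0/(n1 + n0), which is zero if either count is zero. The loss depends on stratum shares and block size, neither of which the SAP gives. Assuming 10% HBeAg-positive, no China split and stratified blocks of five, on average 29.2 of 30 participants are used. Adding an assumed 15% from China gives 28.1 of 30. That is a loss of about one to two participants.

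**The case against.** The strongest reply is that the faulty interval is assumed. Section 5.3.2.1.1 names a test and no interval, and Section 5.5.2.1 asks for a 95% CI without a formula. A stratified Newcombe or score interval would comply with the text and avoid the problem, and the chi-square version of the test would not mislead. This stands: a reader might infer that the SAP prescribes a defective interval, and it does not. It leaves the choice open where both standard Mantel-Haenszel variances fail, which is why a method has to be named.

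Second, under the plan's own assumptions the damage is modest: 1.1% false exclusion if both arms respond at 4%, and 93.7% coverage at 30% vs 4%. This also stands. The 11% to 19% figures need common rates of 10% to 20%. Higher rates are not far-fetched, though. Section 1.4 records that the original re-estimation was meant for a misjudged placebo rate. KSE1 and KSE2 are components of the composite, so their true response rates cannot be below that of the composite.

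Third, the analyses are descriptive and no decision hangs on whether zero is excluded. A reader might infer an inflated formal type I error; Section 1.3 rules that out.

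Fourth, Section 5.5.2.1 already plans per-arm proportions and between-arm differences with 95% CIs, so only the methods are missing. That is correct, and it keeps the fix small.

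Finally, a reader might infer that one-arm strata remove a large part of the ITT set. The SAP gives no stratum shares, and randomisation is stratified by the same two factors, which limits the loss.

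**Conclusion.** The concern holds as a gap that should be fixed, not as a fatal flaw. With about 24 vs 6 and the SAP's 4% placebo rate, the most likely placebo result (78%) is one in which either standard Mantel-Haenszel interval ignores the placebo arm's uncertainty. The lower limit at 7/24 vs 0/6 moves from -0.12 (Newcombe) to 0.11, and zero is excluded from 4/24 instead of 11/24. Wrong exclusion of zero in favour of JNJ-3989 ranges from 1.1% at a common rate of 4% to 19% at 20%.

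These figures rest on the derived 24:6 split, complete data, a single stratum for the enumeration, and use of a Greenland-Robins, Sato or Wald variance. The sentence on adjusted p-values in Section 5.4 is a separate remnant: it conflicts with Section 1.3 but does not bear on the size of this problem.

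**What to change.** In Sections 5.3.2.1.1 and 5.5.2.1, and through them for KSE1 to KSE4:

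1. Name a Newcombe or Miettinen-Nurminen 95% CI for the difference in proportions, stratified, or unstratified if the strata are too sparse, and say how sparseness is judged.
2. Use the same method for pooled Parts 1 and 2. Do not use an interval based on the large-sample Mantel-Haenszel variance for either.
3. Name Wilson or Clopper-Pearson 95% CIs for the per-arm proportions.
4. State how strata with only one arm are handled, and report how many participants contribute to any stratified estimate.
5. Delete the sentence on adjusted p-values in Section 5.4, which conflicts with Section 1.3.

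The cost is SAP wording, one programming change and wider intervals (at 7/24 vs 0/6, width 0.62 instead of 0.36). They are conservative against falsely favouring JNJ-3989. In the other direction, at a common rate of 4%, Miettinen-Nurminen wrongly excludes zero against JNJ-3989 in 9.0% of trials and Newcombe in 1.7%; at 10% the figures are 7.0% and 4.2%. On that count Newcombe is the steadier choice at these arm sizes.
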